3.4. TIMING OF ANALYSIS

A final analysis will be conducted once the last patient completes or discontinues the study, and the resulting clinical database has been cleaned, quality checked, the final database lock has occurred, and the treatments are unblinded.

4. ANALYSIS POPULATIONS

The populations for analysis will include the intent to treat population (ITT), and the safety population (SAF).

4.1. INTENT TO TREAT POPULATION

The ITT population is defined as all randomized patients who receive at least 1 dose of study drug. Patients in this population will be analyzed according to the treatment to which they were randomized, regardless of what treatment they received. All efficacy analyses will be based on this population and treatment assignment.

4.2. SAFETY POPULATION

The SAF is the population of all patients who receive at least 1 dose of study treatment. Patients in this population will be analyzed according to the treatment they received, regardless of which treatment they were randomly assigned. All safety and tolerability analyses will be based on this population and treatment assignment.

5. STATISTICAL METHODS

Descriptive statistical methods will be used to summarize the data from this study, with hypothesis testing performed for selected endpoints. Unless stated otherwise, the term “descriptive statistics” refers to number of patients (n), mean, median, standard deviation (SD), minimum, and maximum for continuous data and frequencies and percentages for categorical data. All data collected during the study will be included in data listings. Unless otherwise noted, the data will be sorted by treatment group, patient number, and by date within each patient number.

The term ‘treatment group’ refers to the three treatment arms of this study: Placebo, 2.5 mg MIN-117, and 5.0 mg MIN-117.

All statistical testing will be two-sided and will be performed using a significance (alpha) level of 0.050 unless stated otherwise, as described in [section 3.3.3](#).

The statistical analyses will be conducted with the SAS[®] System version 9.4 or higher. All analyses will be patient to formal verification procedures. Specifically, results will be verified utilizing independent programming prior to issuance of the draft statistical report. All documents will be verified by the lead statistician to ensure accuracy and consistency of analyses.

5.1. PATIENT DISPOSITION, DEMOGRAPHIC AND BASELINE CHARACTERISTICS

Patient disposition will be presented for all patients. The number of patients who meet all eligibility criteria will be presented, as well as the number of patients included in the ITT,

and safety populations. The number of patients who completed all study treatment and discontinued from the study will be provided. The reasons for early discontinuation at any point also will be presented by treatment group. The proportion of premature discontinuations will be compared between treatment groups using the Fisher exact test. Similarly, the percentages for each discontinuation reason will be compared between treatment groups using the Fisher exact test. Additionally, the number of days on study will be summarized for all treated patients.

Demographic data and baseline characteristics including age, weight, height, body mass index (BMI), gender, and race will be summarized using descriptive statistics for the safety population, and will be presented by treatment group, combined MIN-117 doses, and overall. The number and percent of patients with a current or historical presence of abnormal finding in medical history will be summarized by treatment group and overall. This information will be reviewed for baseline differences, but no statistical testing will be performed.

Baseline disease characteristics, including MADRS, HAM-A, IDS-SR30, CGI-S, SHAPS, DSST, PSS, and A-SEX scores at Baseline will be summarized using descriptive statistics for the safety population, and will be presented by treatment group, combined MIN-117 doses, and overall.

Additionally, study treatment exposure and treatment compliance will be summarized by treatment group. The number of days on study treatment will be summarized for all treated patients. Treatment compliance over the treatment period will be similarly summarized by treatment group. Additionally, treatment compliance between consecutive visits will be summarized by visit and treatment group.

5.2. EFFICACY ANALYSIS

5.2.1. Primary Estimand

The primary estimand, the main clinical quantity of interest to be estimated in the study, is defined by the following components:

Population: patients with a pre-defined minimum threshold and fluctuation of depressive symptoms as captured by IDS-SR₃₀ score before randomization.

Endpoint: change in MADRS total score from Baseline to the end of Week 6.

Measure of Intervention: the effect of the initially randomized treatment that would have been observed had all patients remained on their treatment throughout the double-blind phase.

Intercurrent events: early study discontinuation for any reason.

Summary measure: difference in treatment means.

5.2.2. Primary Efficacy Analysis

MADRS total score values and change from Baseline will be summarized by treatment group and study visit. Change from Baseline in MADRS total score will be analyzed using a mixed-effect model repeated measurement (MMRM) with fixed effects for treatment group (placebo, 2.5 mg MIN-117, and 5.0 mg MIN-117), region, visit, and treatment group-by-visit interaction, a random effect for patient within treatment group, and Baseline MADRS total score as a covariate. An unstructured covariance matrix will be used to model the covariance of within-patient scores. The Kenward-Roger (KR) approximation will be used to estimate denominator degrees of freedom. Comparisons against placebo will be performed using the appropriate contrasts from this model at Week 6.

As a sensitivity analysis of the primary endpoint, change from Baseline to Week 6 in MADRS total score will additionally be analyzed using an analysis of covariance (ANCOVA) model with factors for treatment and region and Baseline MADRS score as a covariate. This analysis will be repeated for change from Baseline to Week 2 and 4 as well. For this analysis, patients missing MADRS total score at any visit will have this value imputed using the LOCF method.

An additional sensitivity analysis of the primary endpoint will be performed to determine the impact of how data missing due to early discontinuation for any reason is handled. This analysis will use the same ANCOVA model described above. This analysis will be repeated for change from Baseline to Week 2 and 4 as well. For this analysis, any MADRS total scores that are missing due to early discontinuation of a subject will be imputed using the value of the mean MADRS total score in the placebo group at that timepoint. All missing MADRS total scores that are not due to early discontinuation will be imputed using the LOCF method.

A final sensitivity analysis of the primary endpoint will be performed using the same ANCOVA model described above, wherein all missing MADRS total scores will be imputed using multiple imputation. Missing values will be imputed using the following auxiliary information: treatment, Baseline MADRS total score, region, sex, Baseline age, and visit. Treatment, Baseline MADRS total score, region, sex, Baseline age, and visit are included as auxiliary information because it is believed that subjects with similar values for each of these parameters would respond similarly. A total of 10 imputations will be performed. The least square (LS) Mean, standard error (SE), LS Mean difference and p-value from the PROC MIANALYZE will be presented. Additionally, the range of p-values from all 10 imputations will be presented.

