10.5.1. Primary Endpoint

The primary efficacy endpoint will be the change in the MADRS total score from Baseline to Week 6. This endpoint will be analyzed using MMRM with treatment arm (5.0 mg MIN-117 dose, 2.5 mg MIN-117 dose, placebo), pooled study center (by country or region based on enrollment), visit, and treatment arm-by-visit interaction as fixed effects, patient nested in treatment as random effect, and Baseline total MADRS score as covariate. An unstructured covariance matrix will be used to model the covariance of within-patient scores. The Kenward-Roger approximation ([Kenward 1997](#)) will be used to estimate denominator degrees of freedom. In this analysis in which the MMRM is fitted to all post-Baseline data, patients in the ITT analysis set who do not have complete data will still contribute to the estimates at Week 6, but will have less weight in the analysis than those patients with complete data (i.e., only the observed cases without imputation of missing values will be used in this analysis). Comparisons against placebo will be performed using the appropriate contrasts from this model at Week 6. An analysis of observed scores available at each visit will also be performed.

The adjustment for multiplicity within the family of primary hypotheses will utilize the conventional Hochberg procedure for the purpose of reporting of results. This procedure will allow the null hypothesis of no treatment difference for both the 5.0 mg and 2.5 mg doses versus placebo to be rejected if largest p-value of comparing either of these 2 doses versus placebo is at or below 0.050. Otherwise, the lowest of these 2 p-values must be at or below 0.025 to allow for rejecting the null hypothesis for the representative dose.

The overall type I error rate for testing the 2 MIN-117 doses versus placebo for the primary and the key secondary endpoint will be controlled at the 2-sided 0.05 level. The primary family of hypotheses (corresponding to the primary endpoint) and the secondary family of hypotheses (corresponding to the key secondary endpoint, the change from Baseline in HAM-A total score) will be tested in a sequential manner with suitable adjustment for multiplicity within the family of primary hypotheses and within the family of the secondary hypotheses such that a MIN-117 dose versus placebo null hypothesis contrast testing within the secondary family can be evaluated only when the same null hypothesis contrast in the primary family was rejected.

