3.1. SAMPLE SIZE AND POWER

The sample size for this study is based on the assumption of a treatment difference of at least 4 points in the mean change from Baseline to to endpoint in MADRS total score between

any MIN-117 dose group and placebo. A standard deviation of 9 in the change in MADRS total score from Baseline is used. Using the Bonferroni multiplicity adjustment for multiple comparisons of 2 MIN-117 dose groups with placebo and assuming an allocation of 2:1:1 for placebo and the 2 MIN-117 doses, 146 patients in the placebo group and 73 patients in each MIN-117 dose group are required to detect the treatment difference of 4 points with a power of 80% at an overall 2-sided significance level of 0.05. When adjusted for a rate of 10% of patients who will not have either Baseline or post-Baseline efficacy assessments, the required number of patients becomes 162 for the placebo group and 81 for each of the 2 MIN-117 dose groups. Therefore, the total number of patients across the 3 treatment groups will be 324.

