3.3. HANDLING OF DATA

3.3.1. Strata and Covariates

The primary efficacy analysis and corresponding sensitivity analyses will have Baseline MADRS as a covariate. Similarly, secondary endpoints and select additional efficacy analyses will contain covariates of their respective Baseline values.

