5.2.4. Key Secondary Efficacy Analysis

HAM-A total score and change from Baseline will be summarized by treatment group and study visit. Change from Baseline in HAM-A total score will be analyzed using an MMRM model with fixed effects for treatment group, region, visit, and treatment group-by-visit interaction, a random effect for patient within treatment group, and Baseline HAM-A total score as a covariate. Comparisons against placebo will be performed using the appropriate contrasts from this model at Week 6.

As a sensitivity analysis of the primary endpoint, change from Baseline to Week 6 in HAM-A total score will additionally be analyzed using an ANCOVA model with factors for treatment and region and Baseline HAM-A score as a covariate. This analysis will be repeated for change from Baseline to Week 2 and 4 as well. For this analysis, patients missing HAM-A total score at any visit will have this value imputed using the LOCF method.

An additional sensitivity analysis of the primary endpoint will be performed to determine the impact of how data missing due to early discontinuation for any reason is handled. This analysis will use the same ANCOVA model described above. This analysis will be repeated for change from Baseline to Week 2 and 4 as well. For this analysis, any HAM-A total scores that are missing due to early discontinuation of a subject will be imputed using the value of the mean HAM-A total score in the placebo group at that timepoint. All missing HAM-A total scores that are not due to early discontinuation will be imputed using the LOCF method.

A final sensitivity analysis of the key secondary endpoint will be performed using the same ANCOVA model described above, wherein all missing HAM-A total scores will be imputed using multiple imputation. Missing values will be imputed using the following auxiliary information: treatment, Baseline HAM-A total score, region, sex, Baseline age, and visit. Treatment, Baseline HAM-A total score, region, sex, Baseline age, and visit are included as auxiliary information because it is believed that subjects with similar values for each of these parameters would respond similarly. A total of 10 imputations will be performed. The least square (LS) Mean, standard error (SE), LS Mean difference and p-value from the PROC MIANALYZE will be presented. Additionally, the range of p-values from all 10 imputations will be presented.

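### The MADRS and HAM-A MMRMs fit one baseline slope to all visits; a baseline-by-visit term would protect Week 6 precision if the slopes differ, at almost no cost

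*SAP*

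**What the plan says.** SAP 5.2.2 models change from baseline in MADRS with treatment group, "region, visit, and treatment group-by-visit interaction, a random effect for patient within treatment group, and Baseline MADRS total score as a covariate". On the within-patient covariance it adds: "An unstructured covariance matrix will be used to model the covariance of within-patient scores". On the test it says: "Comparisons against placebo will be performed using the appropriate contrasts from this model at Week 6".

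Protocol 10.5.1 has the same structure, with pooled center in place of region: "patient nested in treatment as random effect, and Baseline total MADRS score as covariate". SAP 3.3.1 (Strata and Covariates) names no interaction: "The primary efficacy analysis and corresponding sensitivity analyses will have Baseline MADRS as a covariate".

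The key secondary model in SAP 5.2.4 repeats the form for HAM-A: "a random effect for patient within treatment group, and Baseline HAM-A total score as a covariate".

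The schedule has three post-baseline efficacy visits for these scales (Weeks 2, 4 and 6). Neither document adds a baseline-by-visit term to any MMRM. The ANCOVA sensitivity analyses are fitted at a single visit, and of the LOCF version the SAP says: "This analysis will be repeated for change from Baseline to Week 2 and 4 as well". Those analyses therefore do allow a Week 6-specific slope, but only on LOCF, placebo-mean or multiply imputed data.

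**The concern.** With an unstructured covariance and one baseline coefficient, the fitted slope is a precision-weighted average of the visit-specific slopes. Early visits usually carry most of the weight if their residual variance is smaller. If the relation between baseline and change is stronger at Week 6 than at Week 2, the Week 6 means are adjusted with too shallow a slope. Some variation that baseline could explain then stays in the Week 6 residual.

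The stake is precision at the deciding visit. Baseline adjustment matters here because randomization uses permuted blocks with no stratification by severity named (SAP 3.2). Entry severity is set on IDS-SR30, HAM-A and CGI-S, not on MADRS, so the covariate is the plan's only tool against chance imbalance in baseline MADRS. The sizing also has no spare power, as shown under the working.

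**Working it through.** **Plan's own figure.** SAP 3.1 assumes a "treatment difference of at least 4 points in the mean change from Baseline", SD 9, Bonferroni 0.025 two-sided per comparison, 80% power and 2:1 allocation per comparison.
- Normal approximation: placebo n = 9² × (1 + 2) × (2.2414 + 0.8416)² / 4² = 243 × 9.505 / 16 = 144.4, that is 145 placebo and 72.5 per dose.
- Noncentral t at 146 versus 73: power 79.99%. The stated 146/73 reproduces.
- 146/0.9 = 162.2 and 73/0.9 = 81.1, against the stated 162 and 81.

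**Formula for the loss (large sample, complete data).** Let b be the vector of true baseline slopes at Weeks 2, 4 and 6, S the residual covariance matrix, and σ_B the baseline SD.
- Common slope: c = 1′S⁻¹b / 1′S⁻¹1.
- Week 6 residual variance with visit-specific slopes: S₆₆.
- With a common slope: S₆₆ + σ_B²(b₆ − c)².

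**Inputs.** Only the SD of 9 is in the documents, and it is used here for Week 6. Assumed: σ_B 3 to 6; total change SDs 6.5 and 8 at Weeks 2 and 4; residual correlation 0.5 to 0.7 exchangeable, or 0.7 AR(1); and the slopes.

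**One case in full.** Slopes −0.1/−0.3/−0.5, σ_B = 5, exchangeable correlation 0.5.
1. Residual variances: 42.25 − 0.25 = 42.00; 64 − 2.25 = 61.75; 81 − 6.25 = 74.75. SDs 6.481, 7.858, 8.646.
2. With u = 1/SD = 0.1543, 0.1273, 0.1157 (sum 0.3972), the weights are proportional to u(u − 0.25 × 0.3972): 0.00849, 0.00356, 0.00189. Normalized: 0.609, 0.255, 0.136.
3. c = −0.0609 − 0.0766 − 0.0679 = −0.205, less than half the Week 6 slope.
4. Excess: 25 × (−0.5 + 0.205)² = 2.17. Variance 76.92 versus 74.75, or 2.9% larger. The standard error is √1.029 = 1.014 times as large.

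**Excess Week 6 variance from the common slope, over the assumed correlations:**

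| Slopes, Weeks 2/4/6 | σ_B 3 | σ_B 4 | σ_B 5 | σ_B 6 |
|---|---|---|---|---|
| equal | 0% | 0% | 0% | 0% |
| −0.15/−0.25/−0.35 | 0.3–0.4% | 0.5–0.7% | 0.7–1.1% | 1.1–1.6% |
| −0.1/−0.3/−0.5 | 1.0–1.6% | 1.9–2.8% | 2.9–4.4% | 4.2–6.3% |
| −0.2/−0.4/−0.7 | 1.7–2.6% | 3.1–4.6% | 4.9–7.2% | 7.1–10.1% |

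An AR(1) correlation of 0.5 lowers the smallest entry in the three diverging rows to 0.2%, 0.9% and 1.4%.

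**Power.** A parallel grid used change SDs 6/8/9 and 146 versus 73 patients. The interaction gained 0.3 to 1.2 points for slopes −0.1/−0.25/−0.4, 0.5 to 2.1 points for −0.1/−0.3/−0.5, and 1.1 to 4.4 points for 0/−0.3/−0.6 or −0.2/−0.5/−0.8.

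**Simulation with dropout.** N = 324, unstructured covariance, about 8% missing-at-random dropout after each of Weeks 2 and 4, 3% with no post-baseline data, 400 to 600 replicates, both models fitted to the same data.
- Equal slopes: Week 6 standard error 1.3044 with the interaction versus 1.3026 without. It is about 0.13% larger, and smaller in only 20% of trials.
- Slopes −0.20/−0.25/−0.30: 0.06% larger with the interaction, and smaller in 33% of trials.
- Slopes 0/−0.3/−0.6, σ_B 6: 1.2086 with versus 1.2839 without, about 5.9% smaller.
- Bias: at most 0.09 points in absolute value for either model, within simulation error.
- Rejection per comparison under no effect at nominal 0.025, common versus visit-specific: 0.024 versus 0.022 (equal slopes) and 0.020 versus 0.018 (−0.1/−0.3/−0.5).

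The simulation used a fixed 200 degrees of freedom instead of Kenward-Roger. It omitted the patient random effect, because the unstructured matrix already covers within-patient covariance. HAM-A was not calculated separately.

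**The case against.** A pre-specified main-effect baseline covariate is a legitimate choice. Neither document gives a baseline MADRS SD, a slope at any visit, Week 2 or Week 4 SDs, or between-visit correlations, so nothing in them shows that the slopes diverge. With equal or nearly equal slopes the interaction makes the standard error very slightly larger. For HAM-A, the entry threshold of 18 may narrow the baseline spread and shrink any gain. The single-visit ANCOVAs would also show a Week 6 slope. All of this stands, and it keeps the point a refinement.

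It does not remove the point. The ANCOVAs run on imputed data and do not replace the primary test. They also differ from the MMRM in both baseline adjustment and missing-data handling, which blurs the comparison they are meant to offer.

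A reader might infer that the plan adjusts Week 6 with a wrong slope, or that under dropout a misspecified slope contaminates the estimate. The documents do not support either. No slopes are given, baseline is independent of randomized arm, and the simulations with dropout showed no bias or type I error inflation under either model.

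**Conclusion.** The concern holds as a minor, conditional point about efficiency. The models as written impose one baseline slope across Weeks 2, 4 and 6, and the analysis is valid with it. The loss of Week 6 precision is zero if the slopes are equal, roughly 0.3 to 6% of variance for mild to moderate divergence, and up to about 10% in the steepest case at baseline SD 6. These figures rest on assumed baseline SDs, slopes, early-visit SDs and correlations.

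Two stronger statements should be avoided. The interaction does not always tighten the contrast, and its cost is very small but not zero. The loss also should not be expressed as a fixed number of patients: over the assumed range it runs from none to 324 × (1 − 1/1.10) ≈ 29, so any single count only reflects the slopes chosen.

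The case for the change is its asymmetry: about 0.1% in standard error at worst, against a possible gain of several percent, in a trial sized at 79.99% power.

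**What to change.** Before unblinding, add a baseline-by-visit fixed effect to the MMRMs in SAP 5.2.2 (MADRS) and 5.2.4 (HAM-A), and state it in SAP 3.3.1. Record it in SAP section 7 as a change from the model in Protocol 10.5.1.

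Make the same change in SAP 5.2.6 for MMRM endpoints with more than one post-baseline visit: SHAPS, DSST and A-SEX, and the sleep parameters if more than one post-dose recording enters the model. IDS-SR30 and PSS are scheduled only at Week 6 after baseline and do not need it.

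The cost is one model term, 3 − 1 = 2 extra parameters, and about a 0.1% larger Week 6 standard error if the slopes are equal. No new data, visits or patients are needed. Added after unblinding, the term would look data-driven.

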3.3.3. Multiple Testing and Comparisons

The adjustment for multiplicity within the family of primary hypotheses will utilize the Hochberg procedure for the purpose of reporting of results. The procedure will allow the null hypothesis of no treatment difference for both the 5.0 mg and 2.5 mg doses versus placebo to be rejected if the largest p-value of comparing either of these 2 doses versus placebo is at or below 0.05. Otherwise, the lowest of these 2 p-values must be at or below 0.025 to allow for rejecting the null hypothesis for the representative dose.

The overall type I error rate for testing the 2 MIN-117 doses versus placebo for the primary and the key secondary endpoints will be controlled at the 2-sided 0.05 level. The primary family of hypotheses (corresponding to the primary endpoint) and the secondary family hypotheses (corresponding to the key secondary endpoint, the change from Baseline in HAM-A total score) will be tested in a sequential manner with suitable adjustment for multiplicity within the family of primary hypotheses and within the family of the secondary hypotheses such that a MIN-117 dose versus placebo null hypothesis contrast testing within the secondary family can be evaluated only when the same null hypothesis contrast in the primary family was rejected (the truncated Hochberg procedure).

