3.3.4. Missing Data and Outliers

Every effort will be made to obtain required data at each scheduled evaluation from all patients who have been treated. Imputation of incomplete dates is detailed in Section 3.3.5.

As part of sensitivity analyses on the primary and key secondary endpoint, patients who are missing MADRS and HAM-A scores, respectively, will have this value imputed using the

last-observation-carried-forward (LOCF) method and multiple imputation. An additional sensitivity analysis will impute scores missing due to early study discontinuation using the mean score of the placebo group. Additionally, the LOCF method may be used to impute missing MADRS and CGI-I values for the analyses of secondary and exploratory endpoints. Only post-Baseline scores will be eligible to be carried forward for this imputation. The primary analysis will use observed data without imputation.

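### With 10 imputations and no stated seed, the multiple-imputation p-values for MADRS and HAM-A can cross 0.05 or 0.025 by seed alone when they lie near a threshold

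*SAP*

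**What the plan says.** SAP 5.2.2 introduces the analysis in these words: "A final sensitivity analysis of the primary endpoint will be performed using the same ANCOVA model described above". All missing MADRS totals are multiply imputed from treatment, baseline score, region, sex, age and visit. On the number of imputations it says "A total of 10 imputations will be performed". On output it says "LS Mean difference and p-value from the PROC MIANALYZE will be presented", followed by "Additionally, the range of p-values from all 10 imputations will be presented". SAP 5.2.4 repeats this plan for HAM-A.

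Neither section gives a seed, a justification for 10, a Monte Carlo error criterion, or a way to read the range of p-values. SAP 3.3.4 and the programming conventions in SAP 8 do not supply them.

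The confirmatory analysis is separate. SAP 3.3.4 states "The primary analysis will use observed data without imputation", and the Week 6 contrasts come from the MMRM. SAP 3.3.3 applies Hochberg to the two dose comparisons: both are rejected if the larger p-value is at or below 0.05, and otherwise "the lowest of these 2 p-values must be at or below 0.025 to allow for rejecting the null hypothesis" for the dose concerned.

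**The concern.** A pooled estimate from a finite number of imputations is a random quantity, even with the trial data fixed. With 10 imputations both the estimate and the estimated between-imputation variance carry visible simulation noise, and so does the p-value. Without a pre-specified seed, the reported figure is not fixed before unblinding, and the independent programming promised in SAP 5 has no documented seed to reproduce.

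This matters because the other two sensitivity analyses of MADRS fill in single values (LOCF, and the placebo mean combined with LOCF). Multiple imputation is the only one of the three that carries imputation uncertainty into the standard error. Whether it appears to agree with the primary result should not depend on the seed.

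The range of the 10 separate p-values raises a smaller question. Each one treats imputed scores as if they had been observed, and the SAP does not say what a reader should conclude from the range.

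**Working it through.** **Inputs from the documents.** Imputations m = 10 (SAP 5.2.2 and 5.2.4). Thresholds 0.05 and 0.025 (SAP 3.3.3). Difference 4 points, SD 9, 146 placebo and 73 per dose evaluable, 80% power, Bonferroni (SAP 3.1).

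**Assumed.** Fraction of missing information (FMI) of 10%, 20% or 30%, with 5% as a lower check. The documents give no Week 6 dropout rate. The 10% in SAP 3.1 concerns patients lacking baseline or post-baseline assessments, which is a different quantity.

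**Step 1: the plan's own figure.** Per dose, n = 1.5 × 81 × (2.241 + 0.842)² / 16 = 72.2, and placebo is twice that, 144.4. The plan's 73 and 146 give 79.99% power with the noncentral t. Dividing by 0.9 gives 81.1 and 162.2, matching 81 and 162. The sample size reproduces. The plan offers no figure to reproduce for the number of imputations.

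**Step 2: hand check of seed noise.** Scale the limiting total variance (unlimited imputations) to 1, so that between-imputation variance B = FMI and within-imputation variance U = 1 − FMI. The Monte Carlo SD of the pooled z is √(B/m). At FMI 20% and m = 10 this is √0.02 = 0.141. A limiting z of 1.96 then varies over 1.96 ± 1.96 × 0.141 = 1.683 to 2.237, that is p from about 0.092 down to 0.025. This is too narrow, because it holds the variance fixed and uses a normal reference.

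**Step 3: full Rubin's rules by simulation** (400,000 draws per setting). Pooled estimate ~ N(limit, B/m); B_m = B × χ²(m−1)/(m−1); T_m = U + (1 + 1/m)B_m; t reference with Rubin's degrees of freedom. Central 95% range of the reported p-value over seeds:

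| FMI (assumed) | Limiting p 0.05, m=10 | Limiting p 0.05, m=100 | Limiting p 0.025, m=10 | Limiting p 0.025, m=100 |
|---|---|---|---|---|
| 10% | 0.030–0.084 | 0.043–0.059 | 0.014–0.046 | 0.021–0.030 |
| 20% | 0.023–0.109 | 0.039–0.064 | 0.010–0.063 | 0.019–0.033 |
| 30% | 0.018–0.134 | 0.036–0.068 | 0.008–0.082 | 0.017–0.036 |

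Other conventions for the complete-data degrees of freedom move the ends by about 0.003 at most, for example to 0.024–0.111 at 20% and 0.019–0.137 at 30%.

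**Step 4: crossing a threshold from a limiting p that is not exactly on it.** Approximate share of seeds on the wrong side:

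| FMI (assumed) | Limiting p 0.020, reported > 0.025: m=10 / m=100 | Limiting p 0.040, reported > 0.05: m=10 / m=100 |
|---|---|---|
| 5% | 15% / <0.1% | 12% / <0.1% |
| 10% | 27% / 1% | 23% / <1% |
| 20% | 39% / 7% | 35% / 4% |
| 30% | 45% / 14% | 41% / 10% |

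**Step 5: away from a threshold.** At the planned effect, SE = 9 × √(1/146 + 1/73) = 1.29, z = 4/1.29 = 3.10 and p is about 0.002. With m = 10 the reported p exceeds 0.025 in under 0.1% of seeds at FMI 10% and 20%, and in under 1% at 30%. From a limiting p of 0.20 it practically never falls below 0.05.

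**Step 6: the point estimate.** Relative efficiency 1/(1 + FMI/m) at m = 10 is 0.990, 0.980 and 0.971 at FMI 10%, 20% and 30%. The effect estimate is little affected.

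**Step 7: single-imputation p-values.** Each standard error is √(1 − FMI) of the limiting one: 0.949, 0.894 and 0.837, so too small by 5%, 11% and 16%. At FMI 20% with a limiting pooled p of 0.025, the median single-imputation p is 0.012 and the 10 values typically run from about 0.001 to 0.079.

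**The case against.** The strongest reply is that nothing confirmatory rests on this analysis. The Hochberg thresholds govern MMRM contrasts on observed data, HAM-A is likewise tested by MMRM, and no rule makes a claim depend on the multiple-imputation p-value. That stands in full. A reader might infer that the trial's outcome could turn on the seed; the documents rule that out.

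A reader might also infer that the reported output ignores imputation uncertainty. It does not. The pooled PROC MIANALYZE standard error and p-value include between-imputation variance, and the range is only an addition to them. The range itself displays variation between imputations, and the SAP never calls it a measure of robustness. What remains true is narrower: each p-value in the range is too small on average, and the SAP gives no guidance on reading it.

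The ranges in the first table also take a limiting p exactly on a threshold, where any noise falls on both sides. At the planned effect, seed crossings are very rare. That stands too, but the crossing shares from 0.020 and 0.040 show that the effect is not confined to the exact boundary.

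Finally, 100 is not a derived number. From a limiting p of 0.020 at 30% missing information, 14% of seeds still cross 0.025 with 100 imputations. More imputations shrink the noise without removing it. Only a pre-specified seed removes the discretion.

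**Conclusion.** The point holds as a minor, nearly free improvement. With 10 imputations and no seed, the sensitivity p-values for MADRS and HAM-A are not reproducible from the SAP and can change sides of 0.05 or 0.025 when they lie near it. The size depends on the assumed fraction of missing information: from a limiting p of 0.020, roughly a quarter of seeds cross 0.025 at 10% and nearly half at 30%. It also depends on the p-value being close to a threshold; elsewhere the conclusion would not change. The effect estimate loses at most about 3% efficiency over the assumed range. The primary and key secondary decisions are untouched.

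**What to change.** In SAP 5.2.2 and 5.2.4:

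- Pre-specify the random seed.
- Use at least 100 imputations, or state a limit for the Monte Carlo error of the p-value and use enough imputations to meet it.
- Say that interpretation rests on the pooled estimate, standard error, confidence interval and p-value. The confidence interval is not in the current output list and should be added.
- Label the range of single-imputation p-values as descriptive only, noting that each omits between-imputation variance, or drop it.

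The cost is one line of text in each section and minutes of computing. No data collection, sample size or confirmatory test changes.
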